Ab=antibody; ADE=adverse device effect; AE=adverse event; BKZ=bimekizumab; BSA=body surface area; CT=computed axial tomography; DLQI=Dermatology Life Quality Index; ECG=electrocardiogram; eCRF=electronic Case Report Form; HBcAb=anti-hepatitis B core antibody; HBsAg=hepatitis B surface antigen; HBV=hepatitis B virus; HCV=hepatitis C virus; HIV=human immunodeficiency virus; IGA=Investigator's Global Assessment; IGRA=interferon-gamma release assay; IMP=investigational medicinal product; IRT=interactive response technology; P-SIM=Psoriasis Symptom and Impact Measure; PASI=Psoriasis Area and Severity Index; PEOT=Premature End of Treatment; PSD=Patient Symptom Diary; Q4W=every 4 weeks; Q8W=every 8 weeks; scalp IGA=scalp-specific IGA; SFU=Safety Follow-Up; TB=tuberculosis

Note: All assessments should be performed prior to IMP administration. The IMP administration is the starting point for the next administration period. Thus, the assessments in Week 16 and Week 32 belong to the previous treatment period.

^a For visits from the first dose of IMP through Week 32, the visit window is ± 4 days from the scheduled visit. For the SFU Visit, the visit window is ± 7 days from the scheduled visit.

^b The SFU Visit will occur 17 weeks after the final dose of IMP.

^c Ensure no significant changes in medical history.

^d Includes evaluation of signs and symptoms of active TB and risk for exposure to TB.

^e The physical examination will be performed as described in Section 8.2.3.

^f Vital signs (sitting systolic and diastolic blood pressure, pulse rate, and body temperature) are to be measured prior to blood sampling and prior to dosing, where applicable.

^g Pregnancy testing will consist of serum testing at Screening. A urine pregnancy test will be administered at all other visits.

^h Study participants who have evidence of or test positive for hepatitis B or C are excluded from the study, per Exclusion Criterion #9 (Section 5.2). A positive test for HBV is defined as: 1) positive for HBsAg or 2) positive for HBcAb. A positive test for HCV is defined as: 1) positive for anti-HCV Ab and 2) positive via a confirmatory test for HCV (eg, HCV polymerase chain reaction).

ⁱ The HIV test results will not be recorded in the eCRF.

^j Screening chest x-ray/CT scan must occur within 3 months prior to Screening Visit.

Table 1-1: Schedule of Activities

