3 POPULATIONS FOR ANALYSIS

The Enrolled Set (ES) will consist of all study participants who have given informed consent.

The Randomized Set (RS) will consist of all randomized study participants.

The Safety Set (SS) will consist of all study participants who receive ≥ 1 dose of IMP (bimekizumab or placebo).

The Full Analysis Set (FAS) will consist of all randomized study participants who receive ≥ 1 dose of IMP and have a valid measurement for each of the co-primary efficacy endpoints at Baseline.

The Active Medication Set (AMS) will consist of all study participants who receive ≥ 1 dose of active IMP (bimekizumab).

The Maintenance Set (MS) will consist of all study participants who receive ≥ 1 dose of active IMP (bimekizumab) in the Maintenance Treatment Period.

The Per-Protocol Set (PPS) will consist of all study participants in the RS who have no important protocol deviations affecting the co-primary efficacy endpoints. Important protocol deviations

will be predefined, and study participants with important protocol deviations will be evaluated during ongoing data cleaning meetings prior to database lock. The classification of PPS will be determined at blinded data evaluation meeting before unblinding of the data. The classification of study participants with important protocol deviations related to treatment group information will be re-determined after general unblinding.

The Pharmacokinetics Per-Protocol Set (PK-PPS) will consist of all randomized study participants who receive ≥ 1 dose of active IMP (bimekizumab) and provide ≥ 1 quantifiable plasma concentration post dose without important protocol deviations that would affect the concentration.

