4.1.1.2 Analysis periods

The following study periods are defined:

- Screening Period: starts at the time of the informed consent date and ends one day before the first IMP administration.
- Initial Treatment Period (ITP): starts on the day of the first IMP administration and ends prior the first IMP administration in the maintenance treatment period (first IMP in the maintenance treatment period typically occurs at Week 16, but for those that miss the Week 16 IMP administration, first IMP in the maintenance treatment period will be the first IMP administration after Week 16). For study participants that withdraw from the study prior to start of IMP in the maintenance treatment period, the ITP ends on the day of the PEOT Visit. If the PEOT visit is not done, the ITP end date will be set to the date of premature study termination.
- Maintenance Treatment Period (MTP): starts on the day and time of the first IMP administration in the MTP (first IMP in the MTP typically occurs at Week 16 after all clinical and safety assessments have been completed, but for those who miss the Week 16 IMP administration, first IMP in the MTP will be the first IMP administration after Week 16) and ends at the Week 32 visit. For study participants withdrawn from the study after Week 16 but before Week 32, the MTP will end at the PEOT Visit. If the PEOT visit is not done, the MTP end date will be set to the date of premature study termination.
- SFU Period: for participant who complete the study, in other words, complete all scheduled visit, up to and including Week 32, the SFU period starts on the day after Week 32 and ends on the day of the SFU visit. For participants who withdraw early from the study the SFU period start on the day of after PEOT Visit and ends on the day of the SFU visit.

Study participants will be considered to have completed a period if they complete the last scheduled study visit including the respective assessments for that period. It is possible for a study participant to discontinue the study after the Week 16 visit without entering the MTP. Therefore, study participants who discontinue after Week 16 assessments and who never start the MTP will be counted as having completed the ITP but having discontinued the overall study. If study participants miss the Week 16 visit, but start treatment in the MTP, they will still be considered to have completed ITP.

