4.5.1.1 Exposure during the ITP

Definitions for study medication duration (days) and time at risk (days) during the ITP are provided as follows:

Study medication duration (days)

Date of last dose in the ITP – date of first dose in the ITP + 28

The use of +28 reflects the dosing interval of Q4W.

- If the date of last dose in the ITP + 28 days extends to a date beyond the date of first dose of the MTP, then this calculation reverts to:

Date of first dose in the MTP – date of first dose in the ITP + 1

- For study participants who died during the ITP, if date of last dose in the ITP + 28 days extends beyond the date of death, then this calculation reverts to:

Date of death – date of first dose in the ITP + 1

- For study participants who discontinue the ITP early, if date of last dose in the ITP + 28 days extends beyond the date of the last visit (including PEOT, not including SFU), then this calculation reverts to:
 - *Date of last visit – date of first dose in the ITP + 1*

Time at risk (days)

For study participants who complete the final visit of the ITP (Week 16 visit) and continue to the MTP:

$$\text{Date of first dose in the MTP} - \text{date of first dose in the ITP} + 1$$

For study participants who died during the ITP:

$$\text{Date of death} - \text{date of first dose in the ITP} + 1$$

For study participants who discontinue the ITP early or who complete the ITP but not continue to the MTP, use the minimum of the following:

- *The total number of days in the ITP (112 days). For AEs that emerged after 112 days but still within the 119 days window, those AEs would be classified as TEAE, but will be excluded from the output based on the ITP. However, these AEs will be included in the AE summaries for Initial and Maintenance Treatment Period (combined).*
- *Date of last clinical contact – date of first dose in the ITP + 1*

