4.5.3 Additional safety assessments

4.5.3.1 Clinical laboratory evaluations

Laboratory values, including markedly abnormal laboratory values will be presented descriptively by treatment group for the SS.

Tables presenting markedly abnormal values and those based on CTCAE grade (see section 6.13) will only include selected laboratory variables.

For tables where data are summarized by visit, unscheduled and repeat visits will not be summarized, but these data will be included in listings. Assessments collected at SFU visit should be included in by-visit tables. For tables where multiple measurements over a period of time are considered (as in shift tables), unscheduled and repeat visits will be considered as long

as they were collected in the period being summarized. All summaries will be presented in SI units and will be based on observed case values. In the case where laboratory values are below the lower limit of quantification, then these will be set to the midpoint between 0 and the lower limit of quantification for the purpose of summarizing the data. Only central laboratory results will be used in table analysis, while local laboratory results will only be displayed in listings.

For summaries for the ITP and Initial and Maintenance Period (combined) where multiple measurements across different visits are considered (as of markedly abnormal values tables, minimum/maximum post-baseline CTCAE tables, and shift tables), the laboratory results will be attributed according to their sampling date and time at risk for each period (see Section 4.5.1).

The following analyses will be presented:

- A summary of the absolute and change from Baseline values in each laboratory variable by treatment group and visit for the SS displaying the Placebo/BKZ 320mg Q4W and BKZ 320mg Q4W/Q8W.
- A summary of the number and percentage of study participants experiencing markedly abnormal values at any time while on treatment (ie, assessment on or following the first dose of IMP through the last dose of IMP + 119 days, occurring at scheduled and unscheduled visits) by laboratory variable and treatment group. Baseline values and values observed more than 119 days after the last administration of IMP are not considered. Two separate tables will show results for the ITP (for the SS) and the initial and maintenance treatment period (combined) (for the AMS). See section 6.10.1 for the criteria for markedly abnormal values.

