4.5.3.2 Vital signs

The following vital signs variables should be summarized: systolic blood pressure (mmHg), diastolic blood pressure (mmHg), body temperature (°C) and heart rate (beats/min). The following analyses will be provided:

For summaries for the ITP and Initial and Maintenance Period (combined) where multiple measurements across different visits are considered (as of markedly abnormal values tables), the vital sign results will be attributed according to their collection date and time at risk for each period (see Section 4.5.1).

- A summary of the absolute and change from Baseline value for each vital sign variable by treatment group and visit for the SS displaying the Placebo/BKZ 320mg Q4W and BKZ 320mg Q4W/Q8W.

- A summary of the number and percentage of study participants experiencing at least one markedly abnormal value for a vital sign variable as defined in Section 6.10.2, by treatment group. Two separate tables will show results for the ITP (for the SS) and the initial and maintenance treatment period (combined) (for the AMS).
- A by-study participant listing of all vital signs data will be provided for the SS. This listing should be presented by treatment group and will include: center, study participant identifier, age, sex, race, weight, visit, vital sign variable and result.

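### The 112-day cap on Initial Treatment Period time at risk ends one day before the scheduled Week 16 visit for completers who do not enter maintenance, and the stated home for later AEs does not exist for placebo participants never given bimekizumab

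*SAP*

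**What the plan says.** **The cap.** SAP 4.5.1.1 gives ITP time at risk for participants who discontinue the ITP early, or complete it without continuing, as the smaller of two quantities. One is the time from first dose to last clinical contact, counted with +1. The other is a fixed 112 days, with a rule for later events: "The total number of days in the ITP (112 days). For AEs that emerged after 112 days but still within the 119 days window". Those events remain TEAEs but are excluded from ITP output. The SAP then says where they go: "However, these AEs will be included in the AE summaries for Initial and Maintenance Treatment Period (combined"). Participants who continue are counted from first dose to first MTP dose, again with +1.

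**What the cap governs.** SAP 4.5.2.2 assigns TEAEs to a period by onset date and time at risk. For the markedly abnormal, CTCAE and shift tables, SAP 4.5.3.1 says "the laboratory results will be attributed according to their sampling date and time at risk for each period". For markedly abnormal vital signs, SAP 4.5.3.2 says "the vital sign results will be attributed according to their collection date and time at risk for each period".

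**How the period is described elsewhere.** The note to the protocol's Schedule of Activities (1.3) says "Thus, the assessments in Week 16 and Week 32 belong to the previous treatment period". SAP 4.1.1.2 says "study participants who discontinue after Week 16 assessments and who never start the MTP will be counted as having completed the ITP". For those who withdraw before MTP dosing, it ends the ITP at the Premature End of Treatment (PEOT) visit, or at study termination if there is no such visit. It has no 112-day limit.

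**Analysis set.** SAP 4.5 uses the Active Medication Set for combined-period safety summaries. SAP 3 defines it: "The Active Medication Set (AMS) will consist of all study participants who receive" at least one dose of bimekizumab.

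**The concern.** Attending Week 16 is the main way to be counted as an ITP completer, yet for completers who do not continue the clock stops the day before that visit is due. Two participants with the same Week 16 date and the same abnormal value are then treated differently according to whether they were dosed afterwards.

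The tables involved matter. The secondary safety endpoints are TEAEs through Week 16, and the ITP is the only placebo-controlled period. The AE risk differences (SAP 4.5.2.2 and 4.5.2.4) are produced for the ITP alone. Scheduled haematology and biochemistry after Baseline in the ITP fall only at Weeks 4 and 16. A non-continuer seen on Day 113 or later therefore contributes one scheduled post-Baseline sample, not two, to the ITP markedly abnormal, CTCAE and shift tables.

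The second issue is independent of the one-day gap. The SAP assures the reader that events after the cap are tabulated elsewhere, and for one arm that assurance cannot be met.

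**Working it through.** **Inputs**
- Day numbering: date minus first dose + 1 (SAP 4.1.1.1, and the formulas in 4.5.1.1).
- Visit window: ±4 days (protocol 1.3, SAP 4.1).
- Cap: 112 days (SAP 4.5.1.1).
- TEAE window: last dose + 119 days (SAP 4.5.2.1).
- ITP dosing: Baseline and Weeks 4, 8 and 12 (SAP 6.11).
- Planned arms: 90 bimekizumab and 30 placebo (SAP 1.2).

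**Step 1: the plan's own figures.** 16 × 7 = 112 and 17 × 7 = 119. Both are reproduced.

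**Step 2: cap against visit.** Scheduled Week 16 = 112 + 1 = Day 113. Its window is 113 ± 4 = Day 109 to Day 117, which is nine days. The cap ends on Day 112.

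| Week 16 visit day | Within non-continuer's ITP time at risk? |
|---|---|
| 109-112 (4 of 9) | yes |
| 113-117 (5 of 9) | no |

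An on-schedule continuer has 112 + 1 = 113 days. An on-schedule non-continuer has min(112, 113) = 112.

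**Step 3: late TEAEs.** The TEAE window ends on last-dose day + 119.

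| Last ITP dose | Dose day | TEAE window ends | Days after the cap |
|---|---|---|---|
| Baseline | 1 | 120 | 8 |
| Week 4 | 29 | 148 | 36 |
| Week 8 | 57 | 176 | 64 |
| Week 12 | 85 | 204 | 92 |

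For a bimekizumab non-continuer, combined-period time at risk (SAP 4.5.1.3) can run to 119, 147, 175 or 203 days respectively. The combined table therefore recovers all but the last day of the TEAE window. A placebo participant who never enters the MTP belongs to neither the Active Medication Set nor the Maintenance Set. TEAEs after Day 112 in that participant reach no TEAE incidence table.

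**Step 4: size.** One participant is 1/30 = 3.3 percentage points of placebo or 1/90 = 1.1 of bimekizumab. The documents give no rate of non-entry to the MTP, so the rates below are assumptions.

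| Assumed non-entry | Expected placebo | Expected bimekizumab | P(at least one placebo) = 1 − (1 − rate)^30 |
|---|---|---|---|
| 1% | 0.3 | 0.9 | 26% |
| 3% | 0.9 | 2.7 | 60% |
| 5% | 1.5 | 4.5 | 79% |
| 10% | 3.0 | 9.0 | 96% |

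These count non-entrants, not changed table cells. A laboratory or vital-sign cell changes only if the Week 16 visit falls on Day 113 or later and shows an abnormality, or a worse grade, not already counted.

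**Step 5: person-time.** Suppose 2 of 30 placebo participants are on-schedule non-entrants and the rest continue on schedule. The arm has (28 × 113 + 2 × 112)/365.25 = 9.276 participant-years now and (30 × 113)/365.25 = 9.281 if the cap covered Week 16. The issue is which data are counted, not the denominator.

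**The case against.** Much of the case on the other side stands.

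- **Not all Week 16 data are lost.** A reader might infer that non-continuers lose their Week 16 data from every randomised safety table. They do not. The by-visit laboratory and vital-sign tables are on the Safety Set by randomised sequence and nominal visit. The elevated liver-test table covers the whole study. Visits on Day 109-112 and AEs with onset by Day 112 are kept.
- **Late placebo events do not vanish.** All AEs are listed on the Enrolled Set, and discontinuations due to AEs are tabulated on the Randomized Set (SAP 6.3). Placebo participants who continue keep their ITP events up to the switch.
- **Informative loss is not shown.** A reader might infer that the missing finding is the one that kept the participant out of the MTP. The documents do not support that. Week 16 dosing follows that day's assessments, safety laboratory testing is mainly central, and a low neutrophil or lymphocyte count leads to a retest that may allow continuation.
- **No bias between arms is shown.** The cap is the same in both arms, and the combined tables have bimekizumab columns only. Keeping long off-treatment follow-up out of a 16-week comparison is a reasonable and explicit choice.
- **The text is not uniform.** SAP 4.5.3.1 also describes markedly abnormal values as running to last dose + 119 days, and the exclusion sentence in 4.5.1.1 names AEs only. If 112 meant elapsed days, Day 113 would be kept and only Days 114-117 (4 of 9) lost. The +1 formula in the same minimum favours the inclusive count.

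None of this removes the conflict between the cap and the two statements that place Week 16 in the ITP, and none of it rescues the combined-summary sentence for placebo.

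**Conclusion.** Two defects hold as written.

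First, for participants who complete the ITP but do not enter the MTP, the cap excludes Week 16 laboratory and vital-sign values dated Day 113-117, and AEs with onset on those days. The ITP tables affected are TEAE incidence and risk differences; laboratory markedly abnormal, CTCAE and shift tables; and markedly abnormal vital signs. A continuer's same-day pre-dose values are kept, as are AEs up to the date of first MTP dose, apart from the SAP's stated exceptions for acute reactions on the switch date. This contradicts the protocol note on Week 16 and the ITP end in SAP 4.1.1.2.

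Second, the sentence sending AEs after 112 days to the combined summaries is false for placebo participants who never receive bimekizumab.

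The first conclusion rests on the inclusive day count and on the time-at-risk rule prevailing over the other period descriptions in SAP 4.5.3.1. The number affected is unknown and likely small. Each participant is worth up to 3.3 percentage points in a placebo cell or 1.1 in a bimekizumab cell. This should be corrected before the tables are produced; it does not threaten the efficacy conclusions.

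**What to change.** 1. In SAP 4.5.1.1, treat separately those who attend Week 16, or a PEOT visit within the Week 16 window, but do not enter the MTP. Set their ITP time at risk to min{ max[112, visit date − first dose + 1], 117, last clinical contact − first dose + 1 }. Keep the present rule, with 112 days, for earlier discontinuers. The Day 117 bound stops a late PEOT visit from extending ITP follow-up.
2. State that this rule governs the AE, laboratory and vital-sign attribution in SAP 4.5.2.2, 4.5.3.1 and 4.5.3.2. Reconcile it with the period definition in SAP 4.1.1.2 and the protocol note.
3. Limit the combined-summary sentence to participants in the Active Medication Set. Tabulate post-cap TEAEs of placebo participants never given bimekizumab on the Safety Set, for example as a separate row outside the 16-week comparison.

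The cost is one extra derivation, one extra row, and at most five participant-days (117 − 112) for each non-continuer.

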4.5.1.2 Exposure during the MTP

Definitions for study medication duration (days) and time at risk (days) during the MTP are provided as follows:

Study medication duration (days)

$$\text{Date of last active dose in the MTP} - \text{date of first dose in the MTP} + 28$$

The use of 28 days assumes a Q4W dosing interval. This will be adjusted based on the dosing interval (eg, for Q8W use Date of last active dose in the MTP – date of first dose in the MTP + 56 days).

- If the date of last active dose in the MTP + 28 days (or 56 days in the case of Q8W dosing) extends to a date beyond the date of last visit in the MTP (including PEOT, not including SFU), then this calculation reverts to:

$$\text{Date of last visit in the MTP} - \text{date of first dose in the MTP} + 1$$

- For study participants who died during the MTP, if date of last active dose in the MTP + 28 days (or 56 days in the case of Q8W dosing) extends beyond the date of death, then this calculation reverts to:

$$\text{Date of death} - \text{date of first dose in the MTP} + 1$$

Time at risk (days)

For study participants who died during the MTP:

$$\text{Date of death} - \text{date of first dose in the MTP} + 1$$

For study participants who complete the MTP (not including SFU) as scheduled or who discontinue the MTP early, use the minimum of the following:

- $\text{Date of last dose in the MTP} - \text{Date of first dose in the MTP} + 119$
- $\text{Date of last clinical contact} - \text{date of first dose in the MTP} + 1$

